3.8 Audio/Video Recordings or Photographs

1.0 * Please provide a description of the audio and/or visual recordings or photographs and who will have access to them:

The performance test with functional tasks using the default control and VGS control will be video recorded so that they may be viewed by the study team during data analysis to confirm the user performance data collected. Investigators will make every attempt to video record from the neck down to maintain confidentiality; if, however, the subject's face be inadvertently included, investigators will blur out the subject's face during analysis and prior to any future use. Only VAPHS study members will have access to these videos.

The interviews with participants at the end of the study will be audio-recorded for later transcription and data analysis. Only VAPHS study members will have access to these audios.

2.0 * Please describe why this study could not be done without collecting this information in this manner:

Videos will be used to serve as a reference when analyzing the data. Without video, we would not be able to accurately assess user performance during data analysis.

Audios will be used for later transcription and data analysis. Without audio, we would not be able to capture all the comments and suggestions provided by the participants.

3.0 * Please specify your plans for deidentifying or anonymizing the material and when it will be destroyed:

Videos and audios will be captured electronically and files will be named, stored and maintained as described in Section 10: Data Security and Privacy.

ID: Pro00003276

View: 4 Research study methods

Research Study Methods

Describe all study related procedures following enrollment of a subject in this study.

Please see Section 6 for where the study team defines when a subject will be considered enrolled in the study.

1.0

*** Research Procedures/Interventions:**

All research activities will be performed in a controlled environment at the Human Engineering Research Laboratories (Bakery Square Location) or at participants' home by the study investigators comprised of research

engineers, clinicians, and a study coordinator. The testing session will consist of one visit of no more than six hours or can be conducted in multiple lab or home visits of 2-3 hours which add up to no more than 6 hours. If a participant cannot commit to a total of 6 hours, they will be given the option of one 3-hour visit.

Informed consent will be obtained verbally after eligibility screening or onsite. Participants will then complete a questionnaire that includes questions about general demographics, injury and health information, and assistive technology experience. They will also complete a SCI-FI self-care. These two assessments can be done via phone or in-person. In addition, we will administer MoCA, the Paper Folding Test and Cube Comparison Test. SCI-FI Self-care is a validated patient-report outcome measure of physical functioning related to self-care for persons with SCI or other physical disabilities. The Paper Folding Test examines a person's spatial visualization ability by asking him/her to imagine the folding and unfolding of pieces of paper. MoCA is a cognitive screening test designed to assist health professionals in the detection of mild cognitive impairment. The Cube Comparison Test examines a person's spatial orientation ability. These user characteristics may influence their performance with the ARM control.

Participants will go through a training procedure following the training guide provided by Kinova Robotics. During the training phase, a Kinova Gen3 ARM will be mounted onto a table where the training exercises are set up. There will be two training sessions. The first training session will explain the basic operation principle of the ARM, where participants will learn to operate the ARM and practice the basic movements of the adaptive Wolf Motor Function Test (WMFT) for ARM (i.e., move the ARM to table, on top of the box, pick up a cup, simulate drinking, put the cup back to the top of box). They will be given opportunities to try different control interface options. They will start with the method they use to control their power wheelchair and be allowed to explore other options such as the touch interface. This session will last for about one hour. At the end of the training, a pretest will be performed to determine participants' eligibility for the subsequent experimental test procedures. Participants will be asked to perform three simple tasks on a task board including pushing a large round button, flipping a toggle switch, and pushing down a door handle. If participants can complete each task within 2 minutes, they will be considered eligible for participating in the study and move to the next training session. Otherwise, more practice and training will be provided. Investigators may also decide whether a participant has proficient skills to move onto the next session or if the trial should be concluded. The 2nd training session will explain more advanced features of the ARM such as the singularity avoidance system and obstacle avoidance, and we will also introduce the VGS control with fiducial markers and adaptive tools. This session will last approximately 1.5 hours. After training, we will install the ARM to the participants' wheelchairs, on a table, or on an upright stand and configure the control interface for them as needed.

Prior to testing, participants will be asked to rate tasks in a task list in terms of type of assistance needed, levels of difficulty, and levels of satisfaction. They will then be asked to select 5-10 tasks that they cannot complete on their own. They will then complete the selected tasks with two interventions, i.e., default control and VGS control (including fiducial markers and adaptive tools). The tasks will be randomly presented to each participant and the sequence of the two interventions will be counterbalanced using a cross-over design to minimize order and carryover effect. There will be a break after each intervention and participants can also request resting periods at task transitions. The testing session will last about 2 hours. The testing session will be video recorded so that they may be viewed by the study team during data analysis to confirm the user performance measures. We will collect the following measure for each intervention.

- Task completion time: The time it takes to complete each task successfully. A maximum duration will be assigned to each task based on the prior bench-top testing. Participants will be asked to stop the task when the maximum duration is reached.
- Mode Switching Frequency: The number of times a participant has to switch modes for task completion based on logged control commands.
- Robot Pause Time: The total time when the robot is not moving.
- Success rate: The number of tasks out of the selected tasks that can be completed successfully within the maximum assigned time.
- NASA Task Load Index (TLX): NASA TLX will be used to assess the subjective workload of participants after each intervention. It has been shown to be valid and has excellent test-retest reliability. It consists of six dimensions: mental demands, physical demands, temporal demands, performance, efforts, and frustration. Twenty-step bipolar scales are used to obtain ratings on these dimensions, resulting in a score between 0-100. The overall task load index will be a weighted average of all six dimensions, where the weight for each dimension is obtained through pairwise comparisons of these dimensions. The higher score indicates a higher workload.
- System Usability Scale (SUS): SUS will be used to collect perceived ease-of-use after each intervention. It provides a global measure of user satisfaction and has been shown to be reliable and

valid. It consists of 10 statements where users rate on a 5-Likert scale (from 0-strongly disagree to 4-strongly agree). Following a suggested formula, a final score between 0-100 will be obtained. The higher score indicates better usability and overall satisfaction.

At the conclusion of the study, we will conduct a brief semi-structured interview with each participant and obtain more insight on how participants perceive the ease-of-use and usefulness of the VGS control with environment adaptations, and obtain suggestions they may have for further development and deployment. The interviews will be audio-recorded for later transcription.

Please upload a table of procedures if applicable.

The study procedures table must be completed for:

- All Greater than Minimal Risk (GTM) studies; and
- All Minimal Risk studies that use Standard of Care or Usual Care/Interventions.

Name	Modified Date
------	---------------

There are no items to display

2.0

*** Will Usual Care Procedures/Interventions be used?"**

☐ Yes ☒ **No**

If yes, please specify and include a description of what the usual care or expected level of care is at VAPHS (e.g., medications, testing, timing, etc.) for patients, similar to those individuals that meet the inclusion/exclusion criteria for this research study:

2.1 If Usual Care Procedures/Interventions will be used, who is the individual or entity responsible for relevant aspects of the usual care (i.e., which of the above usual care activities will the research study team be responsible for)?:

2.2 Does the usual care at VAPHS for the condition of interest in this research study differ from national guidelines/recommendations (i.e. standard of care)?

☐ Yes ☐ No

If yes, please describe the differences:

2.3 Are any procedures that are considered standard for this patient population performed more frequently than usual care?

☐ Yes ☐ No

If yes, please indicate which time points are considered usual care and which are considered research.

2.4 If there is more than one standard, does VAPHS limit which one is followed (e.g. warfarin use for atrial fibrillation vs. one of the newer anticoagulants).

☐ Yes ☐ No

If yes, please explain:

3.0

*** Does clinical expertise need to be enlisted?**

☐ Yes ☒ **No**

If yes, please provide the provisions for enlisting the services of a clinician with appropriate expertise and privileges to perform duties, if the investigator is not a clinician [i.e. reviewing the data, adverse events,

and new study findings; also making required decisions to protect the health of the subject (e.g., stopping the participant's involvement in the study or determining when to notify the subject or the subject's health care provider of information that may affect the health of the subject)]]:

4.0 Please upload any surveys, questionnaires, and data collection forms.

Document	Description	Version Number
View Cube Comparison(0.01)		0.01
View Interview Quesions(0.01)		0.01
View NASA-TLX(0.01)		0.01
View Paper Folding(0.01)		0.01
View Questionnaire(0.01)		0.01
View Satisfaction(0.01)		0.01
View SUS(0.01)		0.01

ID: Pro00003276

View: 4.1 Research study methods: analysis Plan

1.0 * Please describe the analysis plan for the study (it is acceptable to refer to the sponsor/multi-site protocol for section if applicable):

Statistical analyses will be preceded by a detailed descriptive analysis of the data, using standard descriptive summaries and graphical techniques. The task completion time will be aggregated over the self selected tasks. The key variables including the aggregated task completion time, [mode switching frequency], success rate, NASA TLX score, and SUS score will be examined to ensure that proposed statistical techniques are suitable. Significance level will be determined at 0.05 for all statistical tests. We will first use scatterplots to show each participant's key variables on the two interventions. Different symbols will be used to indicate the order of intervention for each participant and the line of equality will be superimposed for ease of interpretation. We assume neither carry-over nor period effects would be a problem, thus will use a paired t-test to compare the two interventions on all key variables. Qualitative data from the semi-structured interviews will be audio recorded and transcribed, and then analyzed using the affinity diagramming technique to extract themes.

ID: Pro00003276

View: 5 Sub-Studies

1.0 * Is there a sub-study or are there sub-studies associated with this study?

There is no sub-study associated with this study.

ID: Pro00003276

View: 6 Study Population Summary

Study Population Summary

1.0 * What is the maximum number of subjects you plan to enroll at VAPHS?

We aim to recruit a total of 21 participants.

2.0

* Do you plan on enrolling patients into different categories:

☐ Yes ☒ No

If yes, please explain:

3.0 If this is a multi-site study, indicate the projected total subject accrual:

4.0

* Please provide a justification for the sample size:

[Based on our preliminary work, in the lab testing condition, the VGS control could reduce the task completion time by an average of 30% (ranging from 0.03% for the simple door handle task to 55% for the relatively difficult knob turning task). The functional tasks in our task list will contain more complex tasks,

thus we can reasonably assume at least 20% reduction in task completion time when using the VGS control as opposed to the default control for this power analysis.] Given an alpha of 0.05, a 20% reduction in task completion time, and a 25% standard deviation in the difference between the two interventions, we will need 12 participants to obtain 80% power for the study. We will, therefore, recruit 16 participants to account for attrition for the lab testing session. For the home testing session, since this is a pilot study, there is no prior data from our group and published paper. Thus, it is not applicable to calculate a power analysis. We aim to recruit 3-5 participants to assess the feasibility and collect preliminary data. Power analysis was performed using the G*power 3.1.9.2.

ID: Pro00003276

View: 6.1 Study Population

Study Population

1.0 * Check all that apply to describe your study population:

	Study Population
	Non-Veterans
	Special Populations
	Veterans
	Vulnerable populations
	Other

2.0 * Indicate the inclusion criteria for enrollment:

The inclusion criteria are (1) 18 years of age and older; (2) using a power wheelchair as primary means of mobility; (3) having self reported difficulties in performing everyday manipulation tasks such as reaching for a glass of water, opening a refrigerator, and picking up a toothbrush.

3.0 * Indicate exclusion criteria for enrollment:

The exclusion criteria are (1) people with impaired vision; and (2) people with pressure ulcers that prevent them from sitting continuously for an extended period of time.

4.0 If there are any age, ethnic, language, or gender-based exclusion criteria, including the exclusion of any pregnant or lactating women, or those of child-bearing potential, please provide justification:

We would like to recruit participants who are 18 years of age and older, as the control method and tasks are designed for adult users instead of pediatric users.

5.0 Please specify why vulnerable subjects and/or special populations will not be enrolled:

6.0 With some exceptions as listed in VHA Handbook 1200.05, incompetent subjects cannot be enrolled in VAPHS approved research. Specify that you will not enroll incompetent subjects and the general rules to be used in making that determination:

Incompetent subjects will not be enrolled in this study. Competency will be determined based on whether or not the subject is able to provide informed consent by effectively communicating with study investigators.

ID: Pro00003276

View: 6.1.1 Non-Veterans

Non-Veterans

1.0 * Target number of participants:

21

2.0

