1.6.1 Multi-Site Study

1.0 * Is this a multi-site study:

☐ Yes ☒ No

ID: Pro00003276 View: 1.7 Section Chief and Service Line VP approvals

Please upload the approval of the Section Chief, if applicable and the Service Line VP.

1.0 * Institutional Approval Document:
[Request to Conduct Research.pdf\(0.01\)](#)

ID: Pro00003276 View: 2 Study Objectives & Design

Study Summary

1.0 Funding End Date:
3/31/2023

2.0 * Abstract. Please provide a brief description of the study.

The purpose of this study is to evaluate a new control (i.e., the vision-guided shared (VGS) control) for a wheelchair-mounted assistive robotic manipulator among powered wheelchair users. This study will consist of a questionnaire about general demographics, health information, and previous experience with assistive

technology. Several tests will also be administered to test upper extremity function and ability as well as to test spatial orientation and visualization ability. Participants will then undergo a training phase with the assistive robotic manipulator mounted on a table to assess if they will be eligible for participation in the study. Eligible participants will move on to a second training phase where they will be asked to learn and practice slightly more complex tasks while using the vision-guided shared controller. After this training the assistive robotic manipulator will be mounted to the participants wheelchair, a table, or a stand and they will be asked to complete a number of everyday tasks from a task list. At the conclusion of the study, we will conduct a brief semi-structured interview with each participant and obtain more insight on how participants perceive the ease-of-use and usefulness of the VGS control.

3.0 * Describe the study objectives. Please include primary aim and hypothesis, if applicable any secondary aims and hypotheses.

Aim: To evaluate the Vision Guided Shared (VGS) control among 21 powered wheelchair users who will use a wheelchair-mounted ARM to complete a set of functional manipulation tasks.

Hypothesis 1: Subjects will be more efficient when using the VGS control as opposed to the default control, as measured by the number of mode switching, and time taken to complete individual tasks.

Hypothesis 2: Subjects will be more effective when using the VGS control as opposed to the default control, as measured by the number of tasks successfully completed.

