Hypothesis 3: Subjects will report better usability for the VGS control than the default control as measured by the NASA Task Load Index (NASA-TLX) and the System Usability Scale (SUS).

4.0 * Provide a summary of the background of the study, and explain how this research will contribute to existing knowledge. Describe previous studies that provides a basis to show that the proposed research can be carried out without undue risk to human subjects.

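### Five outcomes are each tested at an unadjusted 0.05 with no primary outcome and no rule for combining them, so the error rate of a superiority claim is not fixed by the plan

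*Combined protocol and SAP*

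**What the plan says.** View 4.1, item 1.0 names the outcomes: "The key variables including the aggregated task completion time, [mode switching frequency], success rate, NASA TLX score, and SUS score". It says the team "thus will use a paired t-test to compare the two interventions on all key variables", and sets the threshold: "Significance level will be determined at 0.05 for all statistical tests". The word *including* leaves the list open. Robot pause time is also collected for each intervention (View 4, item 1.0).

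View 2, item 3.0 gives one aim and three hypotheses, all directional in favour of VGS and none ranked:

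- Hypothesis 1 (efficiency) has two measures: "as measured by the number of mode switching, and time taken to complete individual tasks".
- Hypothesis 2 (effectiveness) has one, the number of tasks completed: "Hypothesis 2: Subjects will be more effective when using the VGS control as opposed to the default control".
- Hypothesis 3 (usability) has two, NASA-TLX and SUS.

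View 6, item 4.0 powers one outcome only: "Given an alpha of 0.05, a 20% reduction in task completion time, and a 25% standard deviation in the difference between the two interventions", leading to "we will need 12 participants to obtain 80% power for the study". Sixteen are to be recruited for the lab session to allow for attrition. View 6.1.1, item 2.0, in justifying non-Veteran enrolment, describes the sample as what is needed to show statistically that the VGS control performs better. That is a single overall superiority aim.

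**The concern.** Five tests at 0.05 bear on what View 6.1.1 treats as one claim, and the plan does not say which of them decides it. It also does not say whether Hypotheses 1 and 3 need one significant measure or both. The power statement covers one of the five tests, and the conclusion is not tied to that test. A report could follow the plan exactly and still choose, after seeing the results, which outcome carries the claim. The 0.05 in the plan would then not be the error rate of the claim.

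**Working it through.** **Inputs.** Alpha is 0.05 per test and five paired t-tests are named (View 4.1). The reduction is 20% and the SD of the paired difference 25%; N is 12 for 80% power, with 16 recruited (View 6). Sidedness and the correlation between outcomes are not stated, so both are varied below.

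**1. Reproduce N = 12.** The standardised difference is 0.20/0.25 = 0.80. At n = 12 the noncentrality is 0.80 × √12 = 2.77 on 11 degrees of freedom.

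| Completers | One-sided 0.05 | Two-sided 0.05 |
|---|---|---|
| 11 | 79.5% | 66.8% |
| 12 | 82.9% | 71.4% |
| 14 | 88.2% | 79.0% |
| 15 | 90.3% | 82.1% |
| 16 | 92.0% | 84.8% |

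Twelve is the smallest n that reaches 80% with a one-sided t-test. A two-sided t-test needs 15. Going from 12 to 16 implies 1 − 12/16 = 25% attrition.

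**2. Rule A: any one of five significant results suffices; independent outcomes, no effect on any.**

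- Two-sided, either direction: 1 − 0.95⁵ = 22.6%.
- Two-sided, favouring VGS: 1 − 0.975⁵ = 11.9%.
- One-sided, favouring VGS: 1 − 0.95⁵ = 22.6%.
- Hypothesis 1 alone, either measure sufficing, two-sided and either direction: 1 − 0.95² = 9.8%.

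**3. Rule A with correlated outcomes.** Five equally correlated paired t-tests were simulated under no effect (n = 16, 200,000 replicates for each correlation above zero; the zero row is exact). Results for n = 12 and 21 agree within about 0.3 points.

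| Correlation | Two-sided, either direction | Two-sided, favouring VGS | One-sided, favouring VGS |
|---|---|---|---|
| 0 | 22.6% | 11.9% | 22.6% |
| 0.5 | 18.7% | 9.3% | 17.0% |
| 0.7 | 15.5% | 7.7% | 13.9% |
| 0.9 | 10.6% | 5.3% | 9.8% |
| Nominal, single test | 5% | 2.5% | 5% |

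**4. Rule B: both measures required in Hypotheses 1 and 3.** This is the chance of falsely supporting at least one of the three hypotheses in favour of VGS. For independent outcomes:

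- Two-sided tests: 1 − (1 − 0.025²)² × (1 − 0.025) = 2.6%.
- One-sided tests: 1 − (1 − 0.05²)² × (1 − 0.05) = 5.5%.

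Simulation at n = 12 with correlations from 0 to 0.9 stays at roughly 2.6% to 3.3% two-sided and 5.5% to 6.5% one-sided. Most of this comes from Hypothesis 2, which has a single test.

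**5. Cost of adjusting all five instead.** Bonferroni gives 0.05/5 = 0.01 per test. At a standardised difference of 0.80, 80% power then needs 19 participants one-sided or 22 two-sided. With 16 the power is 71.9% or 60.6%.

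**The case against.** The three hypotheses address distinct constructs, and each could be judged on its own. Hypotheses 1 and 3 join their two measures with *and*, which can fairly be read as requiring both. Under that reading there is almost no inflation (step 4). No sentence in the plan says that any one of five results is enough. This stands: the problem is a missing rule, and its size depends on which rule is meant. It does not remove the point, because the plan does not state the both-measures rule either, and View 6.1.1 treats the evidence as one superiority claim.

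A reader might infer that the plan carries a 15–23% chance of falsely declaring VGS superior. The documents do not support that as a fact. With two-sided tests, 15–23% counts results in either direction, and about half of them favour the default control. It describes false superiority only if every test is one-sided at 0.05, any one result suffices, and the correlation is no higher than about 0.6. Nor is 15% a floor. All five measures come from the same participants doing the same tasks, so high correlation cannot be ruled out.

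It can also be objected that completion time is an imperfect sole primary. View 4 defines it for tasks completed successfully and stops participants at a maximum duration, so the value for a failed task is undefined. That is a fair caution, and it should be settled when the primary outcome is written down. Fixed-order testing, or an explicit both-measures rule, would also control error.

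**Conclusion.** The point holds as a gap in the plan: at least five tests at 0.05, no primary outcome, no adjustment, and no combination rule for Hypotheses 1 and 3. Under the any-one rule, the chance of a false result favouring VGS is about 5% to 12% with two-sided tests against a nominal 2.5%, or about 10% to 23% with one-sided tests against 5%, for correlations from 0.9 down to 0. Under the both-measures rule it is about 3% or 6%, close to nominal. All these rates assume no effect on any outcome and equal correlations. The directional hypotheses and the match of N = 12 to a one-sided test suggest one-sided testing, but the plan does not say so. The gap should be closed before comparative results are examined.

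**What to change.** In View 4.1:

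- Name aggregated task completion time as the single primary outcome, tested at 0.05, and state whether the test is one- or two-sided. Bring Hypothesis 1, which speaks of individual tasks, into line, and say how a task stopped at the maximum duration enters the aggregate.
- Base the superiority conclusion on that outcome alone.
- Make mode switching, success rate, NASA-TLX and SUS secondary, with Holm adjustment across the four, and report 95% confidence intervals for all five.

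The cost is a few sentences and some power on the secondary outcomes. No visit or measurement changes. Naming a primary outcome loses no power in itself, but the choice of sidedness matters. One-sided 0.05 keeps the stated N of 12 (83% power). If two-sided 0.05 is chosen, View 6 must restate power with 12 completers as about 71%; 80% is reached at 15 completers, and all 16 planned lab participants would give about 85%.

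### The crossover analysis has no period term: if performance shifts between the two blocks, the plain paired t-test loses power, and it is biased when the sequences end up unequal

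*Combined protocol and SAP*

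**What the plan says.** View 4.1 (analysis plan, item 1.0) gives the whole inferential method in one sentence: "We assume neither carry-over nor period effects would be a problem, thus will use a paired t-test to compare the two interventions". It applies to every key variable: aggregated completion time, mode switching frequency, success rate, NASA TLX and SUS. Intervention order appears only as a plotting symbol in the descriptive scatterplots. No test has a period or sequence term and no fallback model is named.

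View 4 (Research Study Methods, item 1.0) describes the design. Each participant selects 5 to 10 tasks and does them with both controls, with a break after each, in a testing session of about 2 hours. The "sequence of the two interventions will be counterbalanced using a cross-over design to minimize order and carryover effect". No allocation method is given, and there is no rule for restoring balance after losses.

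**The concern.** The design and the analysis treat order differently. The protocol counterbalances because order could matter; the analysis then assumes that it does not. People who have just been trained on the arm could be faster in the second block through practice, or slower through fatigue.

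Counterbalancing does not remove such a shift from the paired differences. It adds the shift to the default-minus-VGS difference in one sequence and subtracts it in the other. The plain paired t-test counts that spread as noise. If the sequences end up unequal, the shifts no longer cancel in the mean. At stake are the power of a study planned on 12 completers and, after uneven losses, the accuracy of the estimated VGS benefit.

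**Working it through.** **Inputs from the documents.** View 6, item 4.0, gives the effect and spread: "Given an alpha of 0.05, a 20% reduction in task completion time, and a 25% standard deviation in the difference between the two interventions". On the resulting size, the same item says "we will need 12 participants to obtain 80% power for the study", and on losses it says "recruit 16 participants to account for attrition for the lab testing session". View 4.1: "Significance level will be determined at 0.05 for all statistical tests". Sidedness is not stated, although the hypotheses in View 2 are directional ("Subjects will be more efficient when using the VGS control as opposed to the default control"), so both versions are shown.

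**Input assumed.** The period effect π is the change from the first to the second block, in percentage points of completion time. No document gives it. The range used is 0 to 20.

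**Reproducing the plan's figure.** Paired t-test, standardised difference 20/25 = 0.80, exact noncentral t. One-sided, the smallest n with 80% power is 12 (82.9%), which matches the plan. Two-sided, the smallest is 15; power is 71.4% at 12 and 84.8% at 16. The sidedness question is separate and adds no weight to this point.

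**Model.** Let D be default minus VGS, and suppose the second block is faster by π. Then D has mean τ + π for default-first and τ − π for VGS-first, with SD 25 within each sequence.

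- Plain paired t-test: it uses the mean and SD of all D together. Power is simulated, because π is a fixed two-point shift and not normal noise.
- Period-adjusted: the estimate is the average of the two sequence means of D, with SE = (25/2)·√(1/n1 + 1/n2) and n − 2 degrees of freedom. At 6/6, SE = 12.5·√(1/6 + 1/6) = 7.22. At 8/8, SE = 12.5·√(1/8 + 1/8) = 6.25. Neither depends on π.

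**Power (%) for a true 20-point effect, equal sequences**

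| π (points) | 0 | 5 | 10 | 15 | 20 | Adjusted, any π |
|---|---|---|---|---|---|---|
| 6/6, two-sided | 71 | 70 | 65 | 58 | 49 | 70.5 |
| 8/8, two-sided | 85 | 84 | 81 | 75 | 67 | 84.5 |
| 6/6, one-sided | 83 | 82 | 79 | 74 | 67 | 82.4 |

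Under the null at 6/6, the true two-sided size of the plain test is about 3.6% at π = 10 and 1.3% at π = 20, so it is conservative.

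**Bias when sequences are unequal** = π·(n1 − n2)/n.

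- 7/5 at π = 15: 15 × 2/12 = 2.5 points.
- 8/4 at π = 15: 15 × 4/12 = 5.0 points, a quarter of the planned 20.
- 7/5 at π = 5: 5 × 2/12 = 0.8 points.

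At 8/4 with default-first over-represented, the one-sided type I error of the plain test is about 9% at π = 10 and about 11% at π = 15. With VGS-first over-represented it is about 1.4% at π = 10.

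**How likely these splits are.** If 4 of 16 (8/8) are lost at random, there are C(16,12) = 1,820 equally likely sets of completers.

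- 6/6: 28 × 28 = 784, or 43%.
- 7/5 either way: 2 × 8 × 56 = 896, or 49%.
- 8/4 either way: 2 × 1 × 70 = 140, or 8%.

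**Cost of adjusting when π = 0 (two-sided).** 6/6: 71.4 to 70.5, 0.9 points. 8/8: 84.8 to 84.5, under half a point. 7/5: 71.4 to 69.3, about 2 points. 8/4: 71.4 to 65.4, about 6 points.

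**The case against.** The best defence is that the period effect may be small. Participants get about 1 hour of basic training and a timed pretest, with more practice if they fail it, then about 1.5 hours of advanced training that includes VGS. There are breaks, and practice and fatigue pull in opposite directions. Fifteen to 20 points would be 75 to 100% of the whole planned treatment effect. This stands as a limit on size: at 5 points or less the adjustment gains nothing useful. It does not support the assumption itself, for which the plan gives no data.

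The plan also displays order in the scatterplots and says the key variables will be examined for suitability of the techniques. That is a partial safeguard, but it names no alternative analysis and no rule for choosing one.

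The 25% SD might already contain period variation. Then power is not below the planned figure, but adjustment is still more efficient: at 6/6, two-sided, π = 10, the residual SD is √(625 − 100 × 12/11) = 22.7, and power is 73% plain against 78.5% adjusted.

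Three stronger readings are tempting and not supported:

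- That the protocol expects learning between blocks. It counterbalances as a precaution and mentions frustration while learning a new device; it neither predicts nor quantifies a change between blocks.
- That the estimate will be biased. Bias needs both a period effect and unequal sequences.
- That the two blocks are planned for different visits. The statement that the session "can be conducted in multiple lab or home visits of 2-3 hours" covers the programme of up to 6 hours; View 4 describes testing itself as one session of about 2 hours. A same-visit requirement is therefore not part of this point.

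**Conclusion.** The point holds as a low-cost improvement to the analysis plan. It is certain that there is no period term, and that the stated assumption sits awkwardly with the plan's own reason for counterbalancing. The size of the harm is conditional on a period effect that the documents do not give.

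Two-sided, the loss against the adjusted analysis is about 1 point or less at π = 5. At π = 10 it is about 5 points at 6/6 and 4 at 8/8. At π = 15 it is about 12 and 10 points. With equal sequences the paired t-test remains valid but conservative. With unequal sequences the concern is bias, not power: apparent power can even rise, because the estimate is shifted. The more probable 7/5 split gives a modest bias; 8/4 is uncommon under random loss.

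These figures are for completion time only. They assume a common additive period effect, no carry-over and a 25-point SD within sequence.

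**What to change.** In View 4.1, replace the paired t-test for the continuous key variables with the standard two-period crossover analysis: a linear model with treatment and period as fixed effects and participant as a random effect. With complete data this is equivalent to comparing the first-minus-second-block differences between the two sequences and halving the result. Delete the statement that period effects are assumed not to be a problem. Do not add a preliminary test for carry-over: it would have little power at this size, and choosing the analysis on its result distorts the final test.

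The change is wording only. Sequence is already recorded for the scatterplots, and no visit, procedure or sample size has to change. It uses one degree of freedom. The price if there is no period effect is the loss shown in the working, which stays under 1 power point when the sequences are equal and grows with imbalance.
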